11.9 Follow-up

Upon completion of the detoxification phase of the study, patients will be scheduled for continued counseling and follow-up assessments at 1, 3, and 6 months following enrollment. Adverse events, concomitant medication use, and a COWS, ARSW, ASI Lite, CSQ, SF-36, SDR assessment and urine drug test will be recorded at the 1-month follow-up visit. ASI Lite, CSQ, SF-36, and SDR assessments and urine drug tests will be performed at 3 and 6 month follow-up visits. Any SAEs that occurred during this period will be reported to the Lead Investigator, NIDA and to the local IRB. Although follow-up data collection should occur at the specified time point, a window of 30 days after the scheduled due date is allowable for data collection. If necessary self reports can also be collected by telephone.

*Special consideration for the Betty Ford Center: Arrangements will be made so that Betty Ford staff can secure follow-up urine samples in the event the participant's residency is outside the state of California or reasonable distance from the center.

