14.0 ANALYTICAL PLAN

14.1 Statistical Hypotheses

Primary Efficacy Endpoint: It is hypothesized that BUP/NX detoxification, compared to clonidine, will be associated with a better treatment response. A treatment responder is defined as anyone who completes the 13-day detoxification and whose last urine specimen is negative for opiates. By combining treatment retention with opiate abstinence, a composite number is derived that is indicative of both the patients' tolerance to the treatment and the desired outcome of abstinence at the completion of a short-term detoxification procedure. Note that there is no issue concerning the handling of missing data when utilizing this definition of "responder." Patients who fail to either come in or provide a urine sample are, by definition, non-responders.

Other Primary Efficacy Endpoint: Other primary efficacy endpoints were selected to examine the effect of treatment on 1) opiate and other drugs of abuse abstinence throughout the detoxification period and during longer term follow-up, 2) withdrawal symptoms, 3) treatment retention, 4) safety, 5) patient satisfaction with the treatment and 6) extent of ancillary medications dispensed to provide a comprehensive overview of the clinical efficacy and safety of the two treatment regimens.

Hypotheses for the other primary outcome measures include that BUP/NX detoxification, compared to clonidine, will:

- 1. Increase the number and consecutive duration of opiate and all drug-free urine specimens during detoxification and follow-up.
- 2. Increase the number of days retained in treatment.
- 3. Decrease the amount of ancillary medications needed to treat withdrawal symptoms.
- 4. Lessen the severity of withdrawal symptoms as assessed by COWS, ARSW, and VAS.
- 5. Lessen the severity of dependence or abuse as assessed by ASI Lite.

6. Improve the quality of life as assessed by the SF-36 questionnaire and satisfaction with treatment (CSQ).

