14.3 Intent-to-Treat and Evaluable Patient Populations

The intent-to-treat population is defined as the patients who are randomized to treatment. The evaluable population is defined as the patients who are properly qualified to participate in the study in accordance with the inclusion and exclusion criteria and who complete the 13-day detoxification procedure.

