14.4 Analysis Plan

Baseline characteristics of groups will be generated using demographic data from intake questionnaires as well as the Addiction Severity Index. Information summarized will include gender distribution, age, years of use, route of administration, ethnic distribution, education, income, and ASI composite scores. Appropriate 2-sided *t*-tests or chi-square tests will be used to test for equivalence between groups. Inequalities between groups at baseline will be used as cofactors in analyses of outcome variables if related to outcomes.

Each of the primary and other primary outcome measures will be analyzed for the intent-to-treat population. The primary outcome measure is based on an intent-to-treat principle, and therefore cannot be analyzed in the evaluable population. The other primary outcome measures, however, will be analyzed for the evaluable population in addition to the intent-to-treat population. By examining the other primary outcome measures for the evaluable population, the long-term efficacy in treatment responders can be explored. Comparing results from the intent-to-treat and evaluable population analyses will also provide estimates of the effect of missing data. Major differences in the results, if any, will be further explored. While there is every intent to be complete in describing the analyses to be performed, it is not possible to anticipate every contingency, and some adjustments may be required to meet constraints posed by the structure of the data.

The primary outcome measure, treatment responders, will be compared between groups using the Chi-square statistic. Two-group two-tailed t-tests and analysis of variance (with repeated measures where appropriate) will be used to evaluate group differences in other primary outcomes, including retention, number of negative urines and number of consecutive negative urines, and frequency of ancillary medications dispensed. Survival analysis techniques including log- rank statistics will be used to evaluate treatment response over the duration of treatment and follow-up. Both retention in treatment and retention in treatment with negative urine tests for opiates will be evaluated. Repeated measures such as the ASI, VAS, COWS, ARSW will be evaluated using an appropriate repeated measures test such as generalized estimating equations.

Statistical tests will be two-sided, with alpha set at 0.05. Confidence intervals will be two-sided with a 95% confidence coefficient.

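### The gap between intent-to-treat and completers-only results cannot estimate the effect of missing data, because completing detoxification is itself an outcome of treatment

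*Protocol*

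**What the plan says.** Section 14.3 defines two populations. For the first, "The intent-to-treat population is defined as the patients who are randomized to treatment". The second, the evaluable population, is the properly qualified patients "who complete the 13-day detoxification procedure".

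Section 14.4 analyses every primary and other primary outcome by intent to treat and keeps the primary outcome out of the evaluable set. It then adds: "The other primary outcome measures, however, will be analyzed for the evaluable population in addition to the intent-to-treat population". Section 14.2.2 lists 14 such outcomes. Two purposes are given for the second analysis. One is to explore long-term efficacy in patients whom the text calls treatment responders. The other is that "Comparing results from the intent-to-treat and evaluable population analyses will also provide estimates of the effect of missing data".

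Three other places bear on this:

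- Section 14.1 defines the primary endpoint: "A treatment responder is defined as anyone who completes the 13-day detoxification and whose last urine specimen is negative for opiates". One of its hypotheses is that BUP/NX will "Increase the number of days retained in treatment".
- Section 4.0 says that clonidine's side effects, or withdrawal symptoms it leaves unrelieved, can cause patients to leave early.
- Section 11.8 has early terminators complete the day 13 or 14 assessments at their final visit.

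**The concern.** Completion happens after randomisation. By the protocol's own account it is influenced by the assigned drug and by how the patient feels. Two groups of completers are then no longer the groups that randomisation made comparable. The arm that retains more patients also keeps more of those who were struggling.

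The planned contrast would read the resulting gap as the effect of missing data. A reader could conclude that missing data had distorted an intent-to-treat result that was sound. A small gap could equally be taken as reassurance that it does not give. At stake are the 14 other primary outcomes, which section 5.0 combines with the primary objective to judge overall clinical utility.

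**Working it through.** The protocol gives no completion rates and no figure for this contrast, so there is no stated number to reproduce. The check has three parts.

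**1. Does the evaluable set isolate missing data?** It does not.

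- It discards observed data: daily scores before dropout, the final-visit assessments of early terminators (11.8), and all data from patients found ineligible.
- It keeps missing data: a completer can still miss a urine specimen or a follow-up visit.

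**2. Which outcomes remain meaningful among completers?** (14.2.2 and 14.4)

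| Outcome | Among completers |
|---|---|
| 4, days retained (start to last day of treatment) | The same for everyone; zero variance, so the t-test is 0/0 |
| Log-rank test of retention | No events during detoxification |
| 6 and 7, retained and drug-free at each collection | Probability of being retained is 1; only the urine result is left |
| 8, adverse events | Patients who left because of an adverse event are absent |
| Urine counts, COWS, ARSW, VAS, ASI Lite, CSQ, SF-36 | Can be computed, but subject to selection |

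The synopsis describes retention as days on which medication was received. On that definition outcome 4 could vary among completers, but only through missed doses.

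**3. How large can the selection effect be with nothing missing and no treatment effect?**

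Inputs from the protocol: 240 BUP/NX and 120 clonidine patients, two-sided alpha 0.05.

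Assumptions: a standard normal tendency L, with higher values worse; a patient completes if L < c, where c = Φ⁻¹(p) and p is the arm's completion rate; a fully observed standardised outcome Y with correlation r to L; the same mechanism in both arms. The protocol's 20% and 30% response rates (14.6) are lower bounds for completion, because every responder is a completer. They serve as the lowest scenario; the other rates are assumed.

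Formula: E[Y | complete] = −r·φ(c)/p. The spurious BUP/NX minus clonidine difference is therefore r × [φ(c_C)/p_C − φ(c_B)/p_B].

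- 20%/30%: 0.2800/0.20 − 0.3477/0.30 = 1.400 − 1.159 = 0.241; times 0.3 = 0.07, times 0.5 = 0.12.
- 30%/60%: 0.3477/0.30 − 0.3863/0.60 = 1.159 − 0.644 = 0.515; times 0.3 = 0.15, times 0.5 = 0.26.
- 25%/75%: 0.3178/0.25 − 0.3178/0.75 = 1.271 − 0.424 = 0.847; times 0.3 = 0.25, times 0.5 = 0.42.
- 50%/50%: 0.

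Simulation of the same set-up (4,000 trials per cell, t-test at 0.05):

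| Completion, clonidine/BUP-NX | Expected completers | Difference, r = 0.3 to 0.5 | False positives, r = 0.3 to 0.5 |
|---|---|---|---|
| 20%/30% | 24 / 72 | 0.07 to 0.13 SD | 6 to 10% |
| 30%/60% | 36 / 144 | 0.16 to 0.26 SD | 13 to 31% |
| 25%/75% | 30 / 180 | 0.25 to 0.42 SD | 26 to 63% |
| 50%/50% | 60 / 120 | 0.00 SD | about 5% |

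Formula and simulation agree to within 0.01 SD. With r = 0 there is no bias at any completion rate. In every cell the analysis of all randomised patients gives 0.00 SD and about 5% rejections. Where completion differs and r exceeds 0, BUP/NX completers look worse.

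**Label.** A responder needs completion and an opiate-negative last urine (14.1). An evaluable patient needs eligibility and completion (14.3). The sets differ, so the reference in 14.4 to responders is wrong.

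**The case against.** The best defence is that the completer analysis is only supplementary. Intent to treat is applied to every outcome, and the primary outcome is excluded from the evaluable set. Section 14.4 speaks of exploring, and says that major differences will be looked into further. Section 14.5 compares counts of missing observations by arm and tabulates all adverse events without limiting them to completers. A test on a constant yields no result rather than a misleading one. In the model above the bias runs against the trial's hypothesis, and at the only rates the protocol offers it is small. All of this stands and limits the consequence. None of it makes the sentence about missing data true. That sentence is a stated inference and not a detail left to a later analysis plan.

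Three stronger readings are tempting, and the documents do not support them.

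- *The intent-to-treat repeated-measures analyses are biased because they rely on generalized estimating equations.* Section 14.4 says these measures "will be evaluated using an appropriate repeated measures test such as generalized estimating equations". The method is an example, and no working correlation is fixed. A likelihood-based mixed model also fits that wording.
- *Non-completers get no follow-up.* Section 11.9 says "Upon completion of the detoxification phase of the study, patients will be scheduled for continued counseling and follow-up assessments", but this names a phase of the study. The same sentence times the visits from enrollment. The synopsis includes follow-up in each patient's participation, and section 8.0 counts visits from the start of detoxification.
- *A large bias is to be expected.* No completion rates are given, so the upper rows of the table are possibilities and not forecasts.

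**Conclusion.** The point holds, limited to the completers-only comparison and what is inferred from it. The difference between intent-to-treat and evaluable results cannot be read as the effect of missing data: it can be non-zero when nothing is missing, it discards observed data, and it leaves some missingness in place.

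The size is uncertain. With correlation 0.3 to 0.5 and no true effect, it runs from about 0.07 SD at 20%/30% completion to about 0.42 SD at 25%/75%. Equal completion or zero correlation gives none in this model, which assumes the same selection mechanism in both arms.

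One might infer that the trial's main result is compromised. It is not: the primary endpoint counts missing as non-response in all randomised patients, and the intent-to-treat analyses of the other outcomes do not select on completion. This should be corrected, but it does not threaten the primary conclusion.

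**What to change.** In section 14.4:

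1. Delete the sentence that says the comparison of populations estimates the effect of missing data.
2. Make the evaluable analysis descriptive: no between-arm tests, and no retention outcomes (outcome 4, the retention log-rank test, and the retention part of outcomes 6 and 7). Base adverse-event comparisons on a set that does not exclude those who left.
3. Replace treatment responders with completers in the sentence on long-term efficacy.
4. State that the effect of missing data will be examined by sensitivity analyses in all randomised patients. Examples are counting a missing urine as positive, and delta-adjusted multiple imputation for the scales. The details can sit in the statistical analysis plan.

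The cost is a few sentences and a little more analysis work. No patients, visits or assessments are added.

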8.0 STUDY DESIGN

A randomized, open-label, parallel groups study design will be used. After screening and baseline assessments, patients will be stratified for gender and randomly assigned in a 2:1 ratio to either a BUP/NX or clonidine 13-day detoxification. Patients will initiate detoxification in the inpatient setting and, as necessary, will continue detoxification as outpatients for the full 13 days. This typically ranges from 5 to 13 days of inpatient detoxification. After the 13 day detoxification, patients will be assessed for outcome measures including relapse and withdrawal symptoms at follow-up visits occurring 1, 3, and 6 months after starting detoxification. Counseling procedures in existence at each CTP will be used throughout the study. Self-help detoxification handbooks will be distributed to all study participants.

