11.4 Randomization And Enrollment

To qualify for the study, patients are required to meet all inclusion/exclusion criteria. A patient will be included in the study after having been examined by the investigator or study physician who verifies that the inclusion criteria are met and no exclusion criteria are present.

Patients will be assigned randomly once it is determined that eligibility criteria have been met. Randomization to groups will be performed within each site (CTP). Data management for the Pacific Region Node will create randomization envelopes for each site that will be distributed prior to study initiation.

Approximately 60 patients will be enrolled at each of the participating CTP sites for a total of 360 patients. Patients will be assigned to the BUP/NX and clonidine groups using a 2:1 ratio of random assignment. That is, for every patient assigned to receive clonidine, two patients will be assigned to receive BUP/NX. This 2:1 ratio of assignment should facilitate recruitment into the protocols given that patients will have a 66% chance of being assigned to receive BUP/NX. Moreover, the 2:1 assignment will facilitate acquisition of data in a larger cohort of patients on the use of BUP/NX for short-term opiate detoxification.

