14.6 Sample Size Estimate

Sample size and power calculations were made based on the primary outcome measure, treatment response. It was assumed that there would be 20% (maximally) treatment responders in the clonidine group and 30% treatment responders in the BUP/NX group. Using a Chi-Square test power analysis, and assuming a 2:1 buprenorphine:clonidine randomization ratio, an N of 360 is sufficient to detect the 10% difference in number of responders in the two arms with an alpha of 0.05 and a power of 90%. Therefore, the number of patients in the BUP/NX arm is proposed to be 240 and the number in the clonidine arm is to be 120.

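### The primary chi-square ignores the site and gender factors used to randomise, and the cofactor rule beside it leaves the primary analysis not uniquely fixed

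*Protocol*

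**What the plan says.** **Allocation.** Section 8.0 says that "patients will be stratified for gender and randomly assigned in a 2:1 ratio". Section 11.4 adds that "Randomization to groups will be performed within each site (CTP"), using envelopes prepared for each site, and plans the numbers: "Approximately 60 patients will be enrolled at each of the participating CTP sites for a total of 360 patients". Read together, allocation is 2:1 by gender within about six sites.

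**Primary test.** Section 14.4: "The primary outcome measure, treatment responders, will be compared between groups using the Chi-square statistic". No stratum, model or covariate is named. Section 14.6 sizes the trial on a chi-square comparison of two proportions, also without strata.

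**Covariates.** Section 14.4 lists gender, age, years of use, route, ethnicity, education, income and the ASI composites, and says "Appropriate 2-sided *t*-tests or chi-square tests will be used to test for equivalence between groups". It continues: "Inequalities between groups at baseline will be used as cofactors in analyses of outcome variables if related to outcomes". The primary outcome is not exempted from that sentence, and site is not in the list.

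**The concern.** Two things do not fit together.

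1. The design controls site and gender, but the stated primary test uses neither. If response differs between sites, a pooled chi-square still counts the between-site variation as noise although the allocation may have removed it. The test is then less sensitive than the design allows.

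2. Section 14.4 gives two instructions for the primary outcome. One is a chi-square. The other is to bring baseline differences in as cofactors when they relate to outcome. An ordinary chi-square has no place for a cofactor, so once an imbalance is found a reader cannot tell which result is primary. The decision would be made after baseline and outcome data are visible, in a trial that is open-label (sections 8.0 and 10.2).

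The rule also selects poorly. After randomisation, baseline differences between arms arise by chance, so a significance test does not show which variables predict response. The two factors the designers thought worth controlling are the least likely to be adjusted for: gender is balanced by design, and site is not listed.

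**Working it through.** **1. The plan's own figure.** Inputs from sections 14.4 and 14.6: 240 and 120 patients, 30% and 20% response, two-sided alpha 0.05.

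- Pooled rate = (240 × 0.30 + 120 × 0.20)/360 = 96/360 = 0.2667
- Null SE = √[0.2667 × 0.7333 × (1/240 + 1/120)] = 0.0494
- Alternative SE = √[0.30 × 0.70/240 + 0.20 × 0.80/120] = 0.0470
- Power = Φ[(0.10 − 1.96 × 0.0494)/0.0470] = Φ(0.066) ≈ 52.6%

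The stated 90% does not reproduce. That is a separate matter. It enters here only because about 53% is the base from which any gain is counted.

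**2. Pooled chi-square against a stratified test, allocation exactly 2:1 in each stratum.** 100,000 simulated trials per row: six sites of 60, each with 39 patients of one gender and 21 of the other. Overall rates were held at 20%/20% for size and 20%/30% for power. The documents give no site-level response rates and no gender split, so the split and the between-site SD of the log-odds are assumptions. The rows below have no gender effect.

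| Site SD | Clonidine response across sites | Size, chi-square | Size, CMH | Power, chi-square | Power, CMH |
|---|---|---|---|---|---|
| 0 | 20% | 4.9% | 5.0% | 53.4% | 53.2% |
| 0.3 | 13–28% | 4.9% | 5.1% | 53.5% | 54.0% |
| 0.5 | 10–33% | 4.4% | 4.9% | 53.2% | 54.9% |
| 0.8 | 6–42% | 3.9% | 4.9% | 53.2% | 57.6% |
| 1.0 | 4–47% | 3.5% | 5.0% | 53.4% | 59.9% |

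The gain at SD 0.5 is 54.9 − 53.2 = 1.7 points. At SD 1.0 it is 59.9 − 53.4 = 6.5 points. Adding a gender log-odds effect of 0.5 moves these results by about 1 point or less.

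**3. The same comparison without blocking.** Section 11.4 gives a ratio but no block size. With unblocked 2:1 allocation, six sites and an assumed gender odds ratio of 1.3 (40,000 trials per scenario), chi-square size is 5.1%, 5.2%, 5.0% and 5.1% at site SD 0, 0.5, 0.8 and 1.0. The stratified test then gains about 1, 3 and 6 points of power at SD 0.5, 0.8 and 1.0. At SD 0.3 or less it is slightly worse (0.6 points at SD 0.3).

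**4. The cofactor rule.** Section 14.4 lists seven characteristics plus the ASI composites, about 14 candidates. If they are independent, the chance of at least one p<0.05 imbalance is 1 − 0.95^14 = 51%. The rule also requires a relation to outcome. Applying both conditions (14 candidates, 3 of them prognostic; 8,000 null and 4,000 alternative trials; conditional treatment log-odds ratio 0.539, the value implied by 20% and 30%) gives:

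| Covariate log-odds effect per SD | Model changed (null) | Size under rule | Power, chi-square | Power, rule | Power, prespecified adjustment |
|---|---|---|---|---|---|
| 0 | 3.4% | 5.0% | 53.4% | 53.3% | 52.6% |
| 0.3 | 11.4% | 4.9% | 50.2% | 49.9% | 51.3% |
| 0.5 | 16.8% | 4.6% | 46.4% | 46.3% | 51.9% |
| 0.8 | 17.4% | 4.5% | 38.0% | 37.8% | 47.1% |

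Even an analyst who reported the more favourable of the chi-square and the rule's result would reject in 5.1% to 5.4% of null trials. The simulation error is √(0.05 × 0.95/8,000) = 0.24 points, so that is hardly distinguishable from 5%. The rule does little harm to size, but it gives no more power than the plain chi-square.

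**The case against.** The best defence is that an unstratified chi-square is a valid primary test, that stratifying is an efficiency preference, and that such detail can wait for the SAP. A Cochran-Mantel-Haenszel statistic is itself a chi-square statistic, so a SAP could add the strata without contradicting the protocol. Most of this stands for the missing strata. It does not answer the cofactor rule, which the protocol itself states and which its named test cannot carry.

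Five stronger readings are tempting, and the documents do not support them.

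- **That the p-value is miscalibrated in a harmful direction.** Any departure is conservative, and it needs both prognostic sites and balance within strata. Section 11.4's description of two BUP/NX patients for each clonidine patient suggests blocking but does not state it. Block sizes are commonly kept out of protocols, so the omission is not a fault.
- **That site is strongly prognostic.** Some effect is plausible: completing 13 days is part of response, inpatient stay typically runs from 5 to 13 days (section 8.0), and counselling follows each site's practice (section 11.7). But section 7.0 also attributes early discharge to patient choice and insurance, which vary within a site, and keeps discharged patients on the same regimen and procedures.
- **That the model would change in half of all trials.** The 51% omits the relation-to-outcome condition and assumes independent variables. With both conditions the figure was about 3% to 17%.
- **That sections 8.0 and 11.4 contradict each other.** Each names one factor; they are complementary.
- **That stratifying would rescue the power.** It would not come near 90%.

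**Conclusion.** The point holds as a modest defect in stated text. The protocol randomises by gender and within site, names a primary test that uses neither, and adds a covariate rule that this test cannot accommodate. If an imbalance related to outcome appears, the primary analysis is not uniquely defined and would be settled after the data are seen.

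The false-positive rate is not at risk. What may be lost is sensitivity: about 2 to 7 points of power if allocation is blocked and the site log-odds SD is 0.5 to 1.0, about 1 to 6 points if it is unblocked, and essentially nothing at SD 0.3 or less. These sizes rest on assumed site effects and cannot be fixed from the documents. The structural point about the undefined primary analysis does not depend on them. The change should be made because it is nearly free, not because the trial fails without it.

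**What to change.** In section 14.4:

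- Make the primary comparison a Cochran-Mantel-Haenszel test stratified by site and gender, in all randomised patients, reported with a common risk difference and 95% confidence interval.
- Delete the between-arm significance tests of baseline characteristics and the rule that turns their results into cofactors. Keep the descriptive baseline table of section 14.5.
- Name the covariates in advance: site, gender and, for scored outcomes, the baseline value. COWS, ARSW, VAS, ASI Lite and SF-36 are all already scheduled at baseline in Table 1.

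For clarity, name both stratification factors in sections 8.0 and 11.4.

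The cost is protocol and SAP wording; no new data are needed. The statistical price is a power loss of up to about 1 point if sites do not differ and allocation is unblocked. The 90% power statement in section 14.6 needs its own correction.

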14.2.2 Other Primary Outcomes

Other Primary outcomes include:

- 1. The number of urine specimens negative for opiates per patient (a maximum of 4 per patient).
- 2. The number of consecutive urine specimens negative for opiates per patient (maximum of 4).
- 3. The number of urine specimens negative for all drugs (opiates, methadone, cocaine, amphetamines, benzodiazepines, and cannabinoids) per patient (a maximum of 4 per patient).
- 4. The number of days retained in treatment (total days in treatment is the number of days since the start of treatment and the last day of treatment).
- 5. The frequency of dispensing of ancillary medications, by indication (anxiety or restlessness, bone pain or arthralgias, nausea, diarrhea, or insomnia).
- 6. The probability of remaining in treatment and being opiate-free at each urine collection.
- 7. The probability of remaining in treatment and being totally drug-free (negative urine tests for opiates, methadone, cocaine, amphetamines, benzodiazepines, and cannabinoids) at each drug collection.
- 8. The number and severity of adverse events.
- 9. The COWS score during treatment and 1-month follow-up.
- 10. The ARSW score during treatment and 1-month follow-up.
- 11. The VAS score during treatment.
- 12. The ASI Lite score during follow-up.
- 13. The CSQ score at the final visit.
- 14. The SF-36 score during follow-up.

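### Section 14.4 names analysis of variance, which pools the variance, for retention, urine and ancillary-medication outcomes at 240:120, so 95% intervals can miss nominal coverage if the arms differ in spread

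*Protocol*

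**What the plan says.** Section 14.4 states that "Two-group two-tailed t-tests and analysis of variance (with repeated measures where appropriate) will be used to evaluate group differences in other primary outcomes", and lists retention, number of negative urines, number of consecutive negative urines and frequency of ancillary medications dispensed. It adds that "Statistical tests will be two-sided, with alpha set at 0.05" and that confidence intervals will be two-sided at 95%. It does not say whether the t-test is the pooled or the unequal-variance form.

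Allocation is unequal. Section 11.4 says that "Patients will be assigned to the BUP/NX and clonidine groups using a 2:1 ratio of random assignment", and Section 14.6 that "the number of patients in the BUP/NX arm is proposed to be 240 and the number in the clonidine arm is to be 120".

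Section 14.2.2 defines two of the outcomes on bounded scales: "The number of urine specimens negative for opiates per patient (a maximum of 4 per patient"), and days retained, which the 13-day regimen caps. Section 14.1 hypothesises that BUP/NX will increase negative specimens and days retained, and reduce ancillary medication.

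**The concern.** A pooled variance weights each arm's variance by its sample size, whereas the true variance of a difference in means gives more weight to the smaller arm. At 1:1 the two agree. At 2:1 they agree only if the arms have the same spread.

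On bounded and count scales a change in mean usually changes the spread too. If patients in one arm mostly complete 13 days, retention in that arm bunches at the cap. If one arm needs more ancillary medication, its counts usually vary more. So the differences in mean that Section 14.1 expects make unequal spread plausible.

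If the 120-patient clonidine arm is the more variable, pooled intervals are too narrow; if it is the less variable, they are too wide. At stake is the accuracy of the 95% intervals and p-values for several of the other primary outcomes. The main responder comparison is not at stake.

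**Working it through.** **The plan's own figure.** The protocol states no standard deviation, power or interval width for these outcomes, so there is nothing to reproduce for them. Its only such figure is 90% power for the chi-square test (Section 14.6: "It was assumed that there would be 20% (maximally) treatment responders in the clonidine group and 30% treatment responders in the BUP/NX group"). That figure does not reproduce: two-sided power at 240:120 is 52.6%. It is a separate matter and is not used below.

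**Inputs.** n1 = 240 (BUP/NX) and n2 = 120 (clonidine), Section 14.6; two-sided alpha 0.05 and 95% intervals, Section 14.4; urine count 0 to 4, Section 14.2.2; 13-day regimen. The arm standard deviations s1 and s2 are assumed.

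**Formulas.**
- Pooled variance: sp² = (239·s1² + 119·s2²)/358
- Pooled SE = √[sp²·(1/240 + 1/120)]
- True SE = √[s1²/240 + s2²/120]
- k = pooled SE / true SE
- Approximate coverage of a nominal 95% interval = 2Φ(1.96·k) − 1

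**By ratio of standard deviations (clonidine / BUP/NX).**

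| s2/s1 | k | Coverage |
|---|---|---|
| 0.5 | 1.225 | 98.4% |
| 0.8 | 1.076 | 96.5% |
| 1.0 | 1.000 | 95.0% |
| 1.25 | 0.929 | 93.1% |
| 1.5 | 0.879 | 91.5% |
| 2.0 | 0.816 | 89.0% |

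A simulation with normal data, equal means and 10,000 trials per ratio agrees. The pooled test rejects in 1.7% at ratio 0.5, 7.1% at 1.25 and 11.5% at 2.0. The Welch test stays between 4.6% and 5.4% at all ratios tried.

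**Which ratios might these outcomes produce?** The distributions below are illustrative assumptions.

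*Retention:* completers at day 13, all others uniform on days 1 to 12. Example with completion 70% (BUP/NX) v 50% (clonidine): s1 = 3.528, s2 = 4.065, sp² = 13.80. Pooled SE = √(13.80 × 0.0125) = 0.415; true SE = √(12.45/240 + 16.52/120) = 0.435; k = 0.954; coverage 93.9%.

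*Urine count:* Binomial(4, p), variance 4p(1 − p).

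*Ancillary frequency:* a count with either variance equal to the mean or standard deviation proportional to the mean.

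| Outcome and assumption | BUP/NX v clonidine | s2/s1 | Coverage |
|---|---|---|---|
| Retention, completion | 30% v 20% | 0.97 | 95.2% |
| | 50% v 30% | 1.02 | 94.8% |
| | 70% v 50% | 1.15 | 93.9% |
| | 70% v 30% | 1.18 | 93.7% |
| | 80% v 40% | 1.38 | 92.3% |
| | 90% v 30% | 1.86 | 89.6% |
| Urine count, p | 0.3 v 0.2 | 0.87 | 96.0% |
| | 0.6 v 0.2 | 0.82 | 96.4% |
| | 0.6 v 0.4 | 1.00 | 95.0% |
| | 0.8 v 0.5 | 1.25 | 93.1% |
| Ancillary, variance = mean | clonidine mean 1.5 times higher | 1.22 | 93.3% |
| | clonidine mean 2 times higher | 1.41 | 92.0% |
| Ancillary, SD proportional to mean | clonidine mean 1.5 times higher | 1.50 | 91.5% |
| | clonidine mean 2 times higher | 2.00 | 89.0% |

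The direction is not fixed. Under these assumptions ancillary counts, and retention at the larger contrasts, lean towards under-coverage. Urine counts go either way.

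**The case against.** The strongest case against has four parts.

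- **The text does not say equal-variance.** A reader might infer that 14.4 commits to pooled t-tests. It does not: the Welch test is also a two-group two-tailed t-test, and the choice of form is commonly left to the statistical analysis plan, which is not shown. This stands for the t-test. It does not dispose of analysis of variance, which the protocol names itself and which in its ordinary form assumes a common variance, although 14.4 does not say which outcome gets which method.
- **Type I error.** A reader might infer false-positive rates of 8.5% or 11% from standard deviation ratios of 1.5 or 2. Those rates need equal means with unequal spreads. The mechanism here is a shift in mean that changes the spread; if the two distributions are identical, the spreads are equal and the test holds its level. This stands. What remains is coverage, which must hold when the arms differ, as Section 14.1 expects.
- **Size.** The documents give no standard deviations, and at contrasts near those planned for the responder outcome (20% v 30%) the effect is about one percentage point or less and conservative. This stands, and keeps the point minor.
- **Other analyses and flexibility.** Retention is also analysed by survival methods with log-rank statistics, and 14.4 allows adjustments for the structure of the data. The first helps retention, but the plan names no log-rank analysis of the urine-specimen or ancillary counts. Generalized estimating equations are named for measures such as the ASI, VAS, COWS and ARSW, not for these counts. The second names no alternative and leaves the choice until the data are seen.

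**Conclusion.** The point holds as a minor improvement. Section 14.4 names one method that pools the variance, and another whose variance form is unstated, for outcomes where unequal spread is plausible and allocation is 240:120. Pooled 95% intervals would then cover about 92 to 94% for moderate contrasts with a more variable clonidine arm, about 96% when it is less variable, and 89 to 90% only at extreme contrasts, such as 90% v 30% completion or a doubling of both mean and standard deviation of ancillary use. Some contrasts give no error at all. Every figure depends on assumed distributions.

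The documents do not support saying that the standard errors will be wrong, that they err in a known direction, or that the trial's main conclusion is at risk. The primary responder comparison uses a chi-square test and is untouched.

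**What to change.** In Section 14.4, for retention days, urine counts and ancillary-medication frequency, specify the unequal-variance (Welch) t-test, and heteroscedasticity-robust standard errors wherever analysis of variance or a regression model is used. Base the 95% confidence intervals on the same standard errors.

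The cost is a few words and a software option. In a simulation of 20,000 trials at 240:120 with equal variances and a difference of 0.3 standard deviations, power was 75.9% for the pooled test and 75.8% for Welch. No change to sample size, data collection or the primary analysis is needed.
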